## 10.6. Appendix 6: Liver Safety: Suggested Actions and Follow-Up Assessments

### Potential Cases of Drug-Induced Liver Injury

Humans exposed to a drug who show no sign of liver injury (as determined by elevations in transaminases) are termed “tolerators,” while those who show transient liver injury but adapt are termed “adaptors.” In some participants, transaminase elevations are a harbinger of a more serious potential outcome. These participants fail to adapt and therefore are “susceptible” to progressive and serious liver injury, commonly referred to as DILI. Participants who experience a transaminase elevation above  $3 \times$  ULN should be monitored more frequently to determine if they are “adaptors” or are “susceptible.”

In the majority of DILI cases, elevations in AST and/or ALT precede TBili elevations ( $>2 \times$  ULN) by several days or weeks. The increase in TBili typically occurs while AST/ALT is/are still elevated above  $3 \times$  ULN (ie, AST/ALT and TBili values will be elevated within the same laboratory sample). In rare instances, by the time TBili elevations are detected, AST/ALT values might have decreased. This occurrence is still regarded as a potential DILI. Therefore, abnormal elevations in either AST OR ALT in addition to TBili that meet the criteria outlined below are considered potential DILI (assessed per Hy’s law criteria) cases and should always be considered important medical events, even before all other possible causes of liver injury have been excluded.

The threshold of laboratory abnormalities for a potential DILI case depends on the participant’s individual baseline values and underlying conditions. Participants who present with the following laboratory abnormalities should be evaluated further as potential DILI (Hy’s law) cases to definitively determine the etiology of the abnormal laboratory values:

- Participants with AST/ALT and TBili baseline values within the normal range who subsequently present with AST OR ALT values  $>3 \times$  ULN AND a TBili value  $>2 \times$  ULN with no evidence of hemolysis and an alkaline phosphatase value  $<2 \times$  ULN or not available.
- For participants with baseline AST **OR** ALT **OR** TBili values above the ULN, the following threshold values are used in the definition mentioned above, as needed, depending on which values are above the ULN at baseline:
  - Preexisting AST or ALT baseline values above the normal range: AST or ALT values  $>2$  times the baseline values AND  $>3 \times$  ULN; or  $>8 \times$  ULN (whichever is smaller).
  - Preexisting values of TBili above the normal range: TBili level increased from baseline value by an amount of at least  $1 \times$  ULN **or** if the value reaches  $>3 \times$  ULN (whichever is smaller).

Rises in AST/ALT and TBili separated by more than a few weeks should be assessed individually based on clinical judgment; any case where uncertainty remains as to whether it represents a potential Hy's law case should be reviewed with the sponsor.

The participant should return to the investigator site and be evaluated as soon as possible, preferably within 48 hours from awareness of the abnormal results. This evaluation should include laboratory tests, detailed history, and physical assessment.

In addition to repeating measurements of AST and ALT and TBili for suspected Hy's law cases, additional laboratory tests should include albumin, CK, direct and indirect bilirubin, GGT, PT/INR, total bile acids, and alkaline phosphatase. Consideration should also be given to drawing a separate tube of clotted blood and an anticoagulated tube of blood for further testing, as needed, for further contemporaneous analyses at the time of the recognized initial abnormalities to determine etiology. A detailed history, including relevant information, such as review of ethanol, acetaminophen/paracetamol (either by itself or as a coformulated product in prescription or over-the-counter medications), recreational drug, or supplement (herbal) use and consumption, family history, sexual history, travel history, history of contact with a jaundiced person, surgery, blood transfusion, history of liver or allergic disease, and potential occupational exposure to chemicals, should be collected. Further testing for acute hepatitis A, B, C, D, and E infection, liver imaging (eg, biliary tract), and collection of serum samples for acetaminophen/paracetamol drug and/or protein adduct levels may be warranted.

All cases demonstrated on repeat testing as meeting the laboratory criteria of AST/ALT and TBili elevation defined above should be considered potential DILI (Hy's law) cases if no other reason for the LFT abnormalities has yet been found. **Such potential DILI (Hy's law) cases are to be reported as SAEs, irrespective of availability of all the results of the investigations performed to determine etiology of the LFT abnormalities.**

A potential DILI (Hy's law) case becomes a confirmed case only after all results of reasonable investigations have been received and have excluded an alternative etiology.

## 10.7. Appendix 7: ECG Findings of Potential Clinical Concern

ECG Findings That May Qualify as AEs

• Marked sinus bradycardia (rate <40 bpm) lasting minutes.

• New PR interval prolongation >280 msec.

• New prolongation of QTcF to >480 msec (absolute) or by <math>\geq</math>60 msec from baseline.

• New-onset atrial flutter or fibrillation, with controlled ventricular response rate: ie, rate <120 bpm.

• New-onset type I second-degree (Wenckebach) AV block of >30 seconds' duration.

• Frequent PVCs, triplets, or short intervals (<30 seconds) of consecutive ventricular complexes.

ECG Findings That May Qualify as SAEs

• QTcF prolongation >500 msec.

• New ST-T changes suggestive of myocardial ischemia.

• New-onset left bundle branch block (QRS >120 msec).

• New-onset right bundle branch block (QRS >120 msec).

• Symptomatic bradycardia.

• Asystole:

• In awake, symptom-free participants in sinus rhythm, with documented periods of asystole <math>\geq</math>3.0 seconds or any escape rate <40 bpm, or with an escape rhythm that is below the AV node.

• In awake, symptom-free participants with atrial fibrillation and bradycardia with 1 or more pauses of at least 5 seconds or longer.

• Atrial flutter or fibrillation, with rapid ventricular response rate: rapid = rate >120 bpm.

• Sustained supraventricular tachycardia (rate >120 bpm) ("sustained" = short duration with relevant symptoms or lasting >1 minute).

- Ventricular rhythms >30 seconds' duration, including idioventricular rhythm (heart rate <40 bpm), accelerated idioventricular rhythm (HR >40 bpm to <100 bpm), and monomorphic/polymorphic ventricular tachycardia (HR >100 bpm (such as torsades de pointes)).
- Type II second-degree (Mobitz II) AV block.
- Complete (third-degree) heart block.

**ECG Findings That Qualify as SAEs**

- Change in pattern suggestive of new myocardial infarction.
- Sustained ventricular tachyarrhythmias (>30 seconds' duration).
- Second- or third-degree AV block requiring pacemaker placement.
- Asystolic pauses requiring pacemaker placement.
- Atrial flutter or fibrillation with rapid ventricular response requiring cardioversion.
- Ventricular fibrillation/flutter.
- At the discretion of the investigator, any arrhythmia classified as an adverse experience.

The enumerated list of major events of potential clinical concern are recommended as “alerts” or notifications from the core ECG laboratory to the investigator and Pfizer study team, and not to be considered as all inclusive of what to be reported as AEs/SAEs.

## 10.8. Appendix 8: Abbreviations

The following is a list of abbreviations that may be used in the protocol.

Abbreviation	Term
Abs	absolute
ADL	activities of daily living
ADME	absorption, distribution, metabolism, excretion
AE	adverse event
AESI	adverse events of special interest
ALT	alanine aminotransferase
API	active pharmaceutical ingredient
APTT	activated partial thromboplastin time
ARDS	acute respiratory distress syndrome
AST	aspartate aminotransferase
AUC	area under the curve
AUC 24	area under the concentration-time profile from time 0 to 24 hours
AUC inf	area under the concentration-time profile from time 0 extrapolated to infinite time
AUC last	area under the concentration-time profile from time 0 to the time of the last quantifiable concentration
AUMC inf	the area under the first moment curve from time 0 extrapolated to infinite time
AV	atrioventricular
BBS	Biospecimen Banking System
β-hCG	beta-human chorionic gonadotropin
BMI	body mass index
BP	blood pressure
bpm	beats per minute
BUN	blood urea nitrogen
C 24	observed plasma concentration at 24 hours
CFR	Code of Federal Regulations
CIOMS	Council for International Organizations of Medical Sciences
CK	creatinine kinase
CKD-EPI	chronic kidney disease epidemiology collaboration
CL	systemic clearance
C last	predicted plasma concentration at the last quantifiable time point estimated from the log-linear regression analysis
C max	maximum observed concentration
CO 2	carbon dioxide (bicarbonate)
CONSORT	Consolidated Standards of Reporting Trials
COVID-19	coronavirus disease 2019
CRF	case report form

Abbreviation	Term
CRO	contract research organization
CRU	clinical research unit
CSR	clinical study report
CT	clinical trial
CYP	cytochrome P450
DDI	drug-drug interaction
DILI	drug-induced liver injury
DMC	data monitoring committee
DNA	deoxyribonucleic acid
DVT	deep venous thrombosis
EC	ethics committee
ECC	emergency contact card
ECG	electrocardiogram
eCRF	electronic case report form
EDB	exposure during breastfeeding
EDP	exposure during pregnancy
eGFR	estimated glomerular filtration rate
EMA	European Medicines Agency
EU	European Union
EUA	emergency use authorization
EudraCT	European Clinical Trials Database
FAS	full analysis set
FSH	follicle-stimulating hormone
GCP	Good Clinical Practice
GGT	gamma-glutamyl transferase
GLP	Good Laboratory Practice
HBsAg	hepatitis B surface antigen
HCVAb	hepatitis C antibody
HIV	human immunodeficiency virus
HR	heart rate
HRT	hormone replacement therapy
IB	Investigator's Brochure
IBS	irritable bowel syndrome
ICD	informed consent document
ICH	International Council for Harmonisation
ID	identification
IND	Investigational New Drug
INR	international normalized ratio
IP manual	investigational product manual
IPAL	Investigational Product Accountability Log
IRB	Institutional Review Board

Abbreviation	Term
IV	intravenous
$K_{el}$	terminal phase rate constant calculated by a linear regression of the log-linear concentration-time curve
LBBB	left bundle branch block
LFT	liver function test
$\text{Log}_e$	natural logarithm
LPLV	last participant last visit
MCH	mean corpuscular hemoglobin
MCHC	mean corpuscular hemoglobin concentration
MCV	mean corpuscular volume
MRT	mean residence time
msec	millisecond
MTD	maximum tolerated dose
N/A	not applicable
NHP	nonhuman primate
NOAEL	no-observed-adverse-effect level
PCR	polymerase chain reaction
PCRU	Pfizer clinical research unit
PD	pharmacodynamic(s)
PE	physical exam
pH	negative log of the hydrogen ion concentration
PI	principal investigator
PK	pharmacokinetic(s)
PR	pulse rate
PT	prothrombin time
PVC	premature ventricular contraction/complex
QA	quality assurance
QTc	corrected QT
QTcF	corrected QT (Fridericia method)
qual	qualitative
RNA	ribonucleic acid
RT-PCR	reverse transcription polymerase chain reaction
SAE	serious adverse event
SAI	site administration instructions
SAP	Statistical Analysis Plan
SARS-CoV2	severe acute respiratory syndrome coronavirus 2
SoA	schedule of activities
SoC	standard of care
SOP	standard operating procedure
SRSD	single reference safety document
SToD	Study Team on Demand

Abbreviation	Term
SUSAR	suspected unexpected serious adverse reaction
$t_{1/2}$	terminal elimination half-life
TA	technical agreement
TBili	total bilirubin
TEAE	treatment emergent adverse event
$T_{max}$	time for $C_{max}$
ULN	upper limit of normal
US	United States
$V_{ss}$	steady-state volume of distribution following IV infusion
WBC	white blood cell
WHO	World Health Organization
WOCBP	woman/women of childbearing potential
WONCBP	woman/women of non-childbearing potential

1. AMENDMENTS FROM PREVIOUS VERSION(S)

None.

2. INTRODUCTION

[figure not shown]
PF-07304814 is a phosphate prodrug of PF-00835231, a potent and selective inhibitor of the SARS-CoV-2 3CL protease, that is being developed as a constant-rate continuous IV infusion for the treatment of patients hospitalized with COVID-19.

The purpose of this study is to characterize mass balance and further the understanding of PK, metabolism, and elimination of PF-07304814 and PF-00835231 (active moiety). The knowledge of routes of elimination and metabolites is useful for evaluating the likelihood of effects of renal or hepatic impairment on the disposition of PF-07304814 and PF-00835231 (active moiety). The biotransformation analysis will be used to identify metabolites of PF-07304814, if possible. The knowledge gained in this study may guide study designs to address potential drug-drug interactions (DDI) and special population studies.

2.1. Study Design

This is a Phase 1, open-label, single-dose, single-center study to characterize mass balance and evaluate the pharmacokinetics, metabolism, and route and extent of elimination of [¹⁴C]-PF-07304814 in healthy male and female (of non-childbearing potential) participants. The study will enroll approximately 5 healthy participants. Each participant will receive a single, 24-hour constant-rate, continuous IV infusion of 500 mg PF-07304814 containing approximately 420 nCi [¹⁴C] PF-07304814. The total planned duration of participation, from the Screening visit to the last Follow-up phone call, is approximately up to 11 weeks.

Study Schema:

2.2. Study Objectives

2.2.1. Primary Objectives

- To confirm mass balance and characterize the routes of elimination of [¹⁴C]-PF-07304814 and drug related materials following 420 nCi/500 mg dose of [¹⁴C]-PF-07304814.*

- *To evaluate the PK of PF-07304814 and PF-00835231 in plasma and characterize the PK of total [¹⁴C] in plasma.*

2.2.2. Secondary Objectives

- *To identify metabolites of PF-07304814 in plasma, urine and feces, if possible.*
- *To evaluate the safety and tolerability of a single, 24-hour constant-rate, continuous infusion of 500 mg PF-07304814 containing 420 nCi [¹⁴C]-PF-07304814 in healthy participants.*

3. INTERIM ANALYSES, FINAL ANALYSES AND UNBLINDING

No formal interim analysis will be conducted for this study. As this is an open-label study, the sponsor may conduct unblinded reviews of the data during the course of the study for the purpose of safety assessment, facilitating PK/PD modeling, and/or supporting clinical development.

Final analysis will follow the official database release. As this will be an open-label study, there is no formal unblinding of the randomization code.

4. HYPOTHESES AND DECISION RULES

4.1. Statistical Hypotheses

No hypotheses are required.

4.2. Statistical Decision Rules

No decision rules are required.

5. ANALYSIS SETS

5.1. Pharmacokinetic (PK) Analysis Set

5.1.1. Concentration Analysis Set

- *The PK concentration analysis set for PF-07304814 is defined as all participants who receive study intervention and have at least one measurable PF-07304814 and PF-00835231 concentration(s).*
- *The PK concentration analysis set for [¹⁴C] is defined as all participants who receive study intervention and have at least one [¹⁴C] measurement.*

5.1.2. Mass Balance Analysis Set

All participants who receive study intervention and who have evaluable total [¹⁴C] concentration (urinary and fecal) data and who had no protocol deviations or AEs (such as diarrhea or severe constipation) that may have affected the mass balance analysis.

5.1.3. Parameter Analysis Set

The parameter analysis population is defined as all participants randomized and treated who have at least 1 of the parameters of primary interest in plasma, urine or feces.

5.2. Pharmacodynamic Analysis Set

None.

5.3. Safety Analysis Set

All participants who receive at least 1 dose of study medication will be included in the safety analyses and listings.

5.4. Other Analysis Sets

None.

5.5. Treatment Misallocations

This is a nonrandomized study. All participants will receive the same treatment.

5.6. Protocol Deviations

Participants who experience events that may affect their PK profile (eg lack of compliance with dosing) may be excluded from the PK analysis. At the discretion of the pharmacokineticist a concentration value may also be excluded if the deviation in sampling time is of sufficient concern or if the concentration is anomalous for any other reason.

A full list of protocol deviations will be compiled and reviewed to identify major and minor deviations prior to database closure.

5.6.1. Deviations Assessed Prior to Randomization

At Screening, the investigator will assess participants against the inclusion and exclusion criteria as set out in Sections 5.1 and 5.2 of the protocol.

5.6.2. Deviations Assessed Post-Randomization

A full list of protocol deviations for the study report will be compiled prior to database closure. Any significant deviation from the protocol will be reviewed prior to database closure and a decision taken regarding evaluation for each analysis population.

6. ENDPOINTS AND COVARIATES

6.1. Efficacy Endpoint(s)

None.

6.2. Safety Endpoints

An adverse event will be considered a Treatment-Emergent Adverse Event (TEAE) if the event started during the effective duration of treatment. All events that start on or after the first dosing day and time/ start time, if collected, but before the last dose plus the lag time (28 days) will be flagged as TEAEs. The algorithm will not consider any events that started prior to the first dose date. Any events occurring following start of treatment or increasing in severity will be counted as treatment emergent.

Events that occur in a non-treatment period (for example, Follow-up) will be counted as treatment emergent and attributed to the previous treatment taken.

The following data are considered in standard safety summaries (see protocol for collection days and list of parameters):

- *adverse events,*
- *laboratory data,*
- *vital signs data,*
- *ECG results.*

6.3. PK Endpoints

6.3.1. Mass Balance

Carbon-14 in urine will be measured using accelerator mass spectrometry and reported as the percentage of the administered dose of [¹⁴C] excreted at each time interval and as the total percent of dose excreted in urine.

Carbon-14 in feces will be measured using accelerator mass spectrometry and reported as the percentage of the administered dose of [¹⁴C] excreted at each time interval and as the total percent of dose excreted in feces.

Percent recovery of total [¹⁴C] in urine and feces will be determined based on total administered dose.

Individual participant and median data profiles will be graphically presented for the cumulative recovery of [¹⁴C] in urine, feces and their combination. The total recovery of [¹⁴C] in urine, feces and their combination will be listed and summarized. Where possible the rate of excretion of [¹⁴C] will be estimated.

6.3.2. PK Parameter Endpoints

- **Plasma PK Parameters**

Plasma PF-07304814 and PF-00835231 (active moiety) concentrations will be reported in units of mass per volume, while total [^{14}C] in plasma will be reported in units of unchanged drug concentration equivalents per volume (eg, ngEq/mL). PK parameters (Table 1) will be derived from PF-07304814 and PF-00835231 concentrations in plasma and from total [^{14}C] concentration equivalents in plasma. Actual PK sampling times will be used for the derivation of PK parameters.

The PF-07304814 and PF-00835231 concentrations and PK parameters and the total [^{14}C] concentration equivalents and PK parameters will be listed and summarized using descriptive statistics. Individual and median PF-07304814 and PF-00835231 concentration-time profiles and total [^{14}C] concentration equivalents-time profiles will be graphically presented.

Table 1. Noncompartmental PK Parameters of Plasma

Parameter	Analysis Scale	PF-07304814	PF-00835231	total [^{14}C]
AUC _{inf} ^a	ln	D	D	D
AUC _{last} ^a	ln	D	D	D
C _{max}	ln	D	D	D
T _{max}	R	D	D	D
C ₂₄	R	D	D	D
t _{1/2} ^a	R	D	D	D
CL ^{a,b}	ln	D		
V _{ss} ^{a,b}	ln	D		

Key: a=if data permits, b=PF-07304814 only, D=displayed with descriptive statistics, ln=natural-log transformed, R=raw (untransformed)

- **Urine PK Parameters**

Total urine [^{14}C] concentrations and percent [^{14}C] will be listed and summarized using descriptive statistics. Individual and summary profiles of urine [^{14}C] will be graphically presented.

Data permitting, following urine parameters will be calculated:

Table 2. Noncompartmental PK Parameters of Urine

Parameter	Analysis Scale	PF-07304814	Total [^{14}C]
Total [^{14}C] Urine	R	D	D
% [^{14}C] Urine	R	D	D

6.3.3. Metabolic Profiling and Metabolite Identification

Plasma, urine, and fecal samples will be analyzed for identification of metabolites of PF-07304814, if possible. Results of the metabolic profiling analysis will be detailed in a separate report and will be summarized in the CSR.

6.3.4. PD Endpoints

None.

6.4. Covariates

None.

7. HANDLING OF MISSING VALUES

For the analysis of safety endpoints, the sponsor data standard rules for imputation will be applied.

7.1. Concentrations Below the Limit of Quantification

In all data presentations (except listings), concentrations below the limit of quantification (BLQ) will be set to zero. (In listings BLQ values will be reported as “<LLQ”, where LLQ will be replaced with the value for the lower limit of quantification).

7.2. Deviations, Missing Concentrations and Anomalous Values

In summary tables and plots of median profiles, statistics will be calculated having set concentrations to missing if 1 of the following cases is true:

1. A concentration has been collected as ND (ie, not done) or NS (ie, no sample).
2. A deviation in sampling time is of sufficient concern or a concentration has been flagged anomalous by the pharmacokineticist.

Note that summary statistics will not be presented at a particular time point if more than 50% of the data are missing.

7.3. Pharmacokinetic Parameters

Actual PK sampling times will be used in the derivation of PK parameters.

If a PK parameter cannot be derived from a participant's concentration data, the parameter will be coded as NC (ie, not calculated). (Note that NC values will not be generated beyond the day that a participant discontinues).

In summary tables, statistics will be calculated by setting NC values to missing; and statistics will be presented for a particular renal function group with ≥ 3 evaluable measurements.

If an individual participant has a known biased estimate of a PK parameter (due for example to an unexpected event such as vomiting before all the compound is adequately absorbed in the body), this will be footnoted in summary tables and will not be included in the calculation of summary statistics or statistical analyses.

8. STATISTICAL METHODOLOGY AND STATISTICAL ANALYSES

8.1. Statistical Methods

The PK data will be summarized using descriptive statistics.

8.2. Statistical Analyses

8.2.1. Pharmacokinetic Analysis

The PK parameters detailed in [Section 6.3](#) will be listed and summarized for participants in the appropriate analysis sets (as defined in [Section 5.1.2](#)). Missing values will be handled as detailed in [Section 7](#).

PK parameters will be summarized as specified in the table below.

Table 3. PK Parameters to be Summarized Descriptively

Parameter	Summary Statistics
AUC _{last} , AUC _{inf} , C _{max} , CL and V _{ss}	N, arithmetic mean, median, cv%, standard deviation, minimum, maximum, geometric mean and geometric cv%.
T _{max}	N, median, minimum, maximum.
t _{1/2}	N, arithmetic mean, median, cv%, standard deviation, minimum, maximum.

Box and whisker plots for individual participant parameters (AUC_{inf}, AUC_{last} and C_{max}) be presented and overlaid with geometric means.

Supporting data from the estimation of t_{1/2} and AUC_{inf} will be listed: terminal phase rate constant (k_{el}); goodness of fit statistic from the log-linear regression (r²); the percent of AUC_{inf} based on extrapolation (AUC_{extrap} %); and the first, last, and number of time points used in the estimation of k_{el}. This data may be included in the clinical study report.

Presentations for PK concentrations will include:

- A listing of all concentrations sorted by participant id and nominal time postdose. The listing of concentrations will include the actual times. Deviations from the nominal time will be given in a separate listing.

- A summary of concentrations by nominal time postdose, where the set of statistics will include n, mean, median, standard deviation, coefficient of variation (cv) and the number of concentrations above the lower limit of quantification.
- A plot of median PK and radioactivity concentrations against nominal time postdose (based on the summary of concentrations by time postdose), where the median concentration-time profiles for plasma PK, and plasma radioactivity, will be presented together on the same plot.
- A log-linear plot of the median concentrations against nominal times postdose, as described above.
- Plots of individual concentrations against actual time postdose, where profiles for plasma PK will be presented together on the same plot.
- Log-linear plots of individual concentrations against nominal times postdose, as described above.

For summary statistics, median and mean plots by sampling time, the nominal PK sampling time will be used, for individual participant plots by time, the actual PK sampling time will be used.

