## 3. OBJECTIVES AND ENDPOINTS

Objectives	Endpoints
Primary:	Primary:

To confirm mass balance and characterize the routes of elimination of [C]-PF-07304814 and drug related materials following 420 nCi/500 mg dose of [C] PF-07304814

To evaluate the PK of PF-07304814 and PF-00835231 in plasma and characterize the PK of total [C] in plasma

	

Amount of [C] recovered in urine and feces, as a percent of the total [C] dose administered

Plasma PK parameters, including AUClast, AUCinf, Cmax, Tmax, C24, CL, Vss, and t1/2

Total [C] in plasma and PK of PF-07304814 and PF-00835231 in plasma

Secondary Objective:	Secondary:

To identify metabolites of PF-07304814 in plasma, urine and feces, if possible

To evaluate the safety and tolerability of a single, 24-hour constant-rate, continuous infusion of 500 mg PF-07304814 containing 420 nCi [C]-PF-07304814 in healthy participants

	

Identification and determination of relative abundance of the metabolites of PF-07304814 in plasma, urine, and feces

Assessment of TEAEs, clinical laboratory abnormalities, vital signs, physical exam, and 12-lead ECGs.

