8.3.1. Treatment and Disposition of Participants

Participant evaluation groups will show end of study participant disposition and will show which participants were analyzed for pharmacokinetics, as well as for safety (adverse events and laboratory data). Frequency counts will be supplied for participant discontinuation(s).

Data will be reported in accordance with the sponsor reporting standards.

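### SAP 8.2.1 ties the plasma PK parameters to the Mass Balance Analysis Set (5.1.2) instead of the Parameter Analysis Set (5.1.3)

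*SAP*

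**What the plan says.** SAP 8.2.1 (Pharmacokinetic Analysis) is the only sentence that assigns an analysis set to the PK parameters. It says that the parameters of Section 6.3 "will be listed and summarized for participants in the appropriate analysis sets (as defined in [Section 5.1.2". Three sets stand under SAP 5.1:

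- 5.1.1 covers concentrations.
- 5.1.2 is the Mass Balance Analysis Set. It takes treated participants with evaluable urinary and fecal 14C "who had no protocol deviations or AEs (such as diarrhea or severe constipation) that may have affected the mass balance analysis". It contains no plasma criterion.
- 5.1.3 is the Parameter Analysis Set: "all participants randomized and treated who have at least 1 of the parameters of primary interest in plasma, urine or feces".

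Section 6.3 covers both mass balance (6.3.1) and the plasma and urine PK parameters (6.3.2). Table 3, which follows the citation in 8.2.1, holds AUClast, AUCinf, Cmax, CL, Vss, Tmax and t1/2, all of them plasma parameters. Protocol Section 3 lists "Plasma PK parameters, including" these quantities among the primary endpoints. Protocol 9.2 defines concentration and mass balance sets but no parameter set.

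**The concern.** The set cited for the parameter tables is defined by other matrices. A participant with a complete plasma profile would leave the plasma parameter listings and summaries if a fecal collection were not evaluable, or if diarrhea or a deviation might have affected mass balance. The drug is infused intravenously, so such an event does not by itself make the plasma profile invalid.

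That 5.1.3 goes uncited would be minor on its own, since Section 8 does not cite 5.1.1 or 5.3 either. The problem is that a different set is cited in its place. The N of a primary table then depends on whether the programmer follows the section number or the apparent intent, and in an open-label study that choice could be made after the data have been seen.

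**Working it through.** The plan gives no figure to reproduce. The check compares the sections and then counts participants.

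**1. What the citation fits.** Section 5.1.2 is the right set for 6.3.1 (Mass Balance). It does not fit the plasma part of 6.3.2 or Table 3. The plural (analysis sets) does not match a section that defines one set, which points to a wrong or incomplete number and not to an intended restriction.

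**2. Whether other text settles it.** SAP 5.6.2 requires, before database closure, "a decision taken regarding evaluation for each analysis population". SAP 8.3.1 says that the evaluation groups "will show which participants were analyzed for pharmacokinetics". Both make a discrepancy easier to notice, but neither says which set serves which table.

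**3. Direction of the effect.** A participant with evaluable urinary and fecal 14C should have at least one primary parameter in urine or feces. The Mass Balance set should therefore lie inside the Parameter set, if the latter is read as all treated participants. Following the citation can then only remove participants from the plasma tables.

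**4. Size.** Inputs: about 5 enrolled, with replacement permitted when fully evaluable participants fall below 4 (Protocol 9.5); statistics presented with at least 3 evaluable measurements (SAP 7.3). The SAP 7.3 rule is worded for renal function groups, which this study does not have, so its use here is an assumption. Fraction lost = exclusions / 5.

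| Excluded | Fraction lost | N left | Below 4, replacement permitted? | At least 3, summarized? |
|---|---|---|---|---|
| 1 | 1/5 = 20% | 4 | no | yes |
| 2 | 2/5 = 40% | 3 | yes | yes |
| 3 | 3/5 = 60% | 2 | yes | no, unless replaced |

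Protocol 4.1 ties replacement to the number of completed participants. Under that wording, someone who completes the study but had diarrhea might not count toward replacement at all.

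**5. Likelihood.** The documents give no rate of exclusion from the Mass Balance set. With an assumed independent rate q, the chance of losing at least one of five is 1 − (1 − q)^5:

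- q = 5%: 1 − 0.95^5 = 22.6%
- q = 40%: 1 − 0.60^5 = 92.2%

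The range is too wide to support a probability statement, and none is made.

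**6. After correction.** With the plasma parameters assigned to 5.1.3, the number leaving the plasma tables for a urine or fecal reason is 0 of 5.

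**The case against.** The strongest reply is that this is a clerical slip whose intent can be recovered. SAP 5.6 has its own rule for excluding participants whose PK profile may be affected. SAP 7.3 deals with biased or non-derivable parameters. SAP 6.3.2 and Protocol 9.3.1.2 describe the plasma summaries without any mass balance restriction. Protocol 9 requires major changes to primary analyses to appear in an amendment, and none does. The study is descriptive, and it already plans for about 4 participants with complete plasma, urine and fecal collections, so even the literal reading gives a table near the planned size.

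Most of this stands. It makes a deliberate filter unlikely and keeps the consequence small. Incomplete is also a fair description, because 5.1.2 suits 6.3.1. But none of these passages names the set for the parameter tables, while 8.2.1 does name one.

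A second objection is that assigning the urine 14C parameters to 5.1.2 also filters across matrices: a participant with complete urine but non-evaluable feces loses a valid urine value. That is true. However, the SAP itself places 14C "as the total percent of dose excreted in urine" under Mass Balance in 6.3.1, and the percent of 14C in urine in Table 2 is the same quantity. Using one set avoids reporting it with two different Ns.

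A third objection is that Protocol 6.3.1 mentions a randomization schedule, so the wording of 5.1.3 need not exclude anyone. SAP 5.5 says the opposite: "This is a nonrandomized study. All participants will receive the same treatment". Defining the set by treatment alone works under either description.

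**Conclusion.** The concern holds. SAP 8.2.1 cites a set that does not fit the plasma parameters it governs, and no other text supplies the right one. It is probably a citation error and not an intended restriction; the harm arises only if it is programmed as written. In that case each exclusion costs 20% of a primary table of about 5. With one or two exclusions the table is smaller but still present, and only a third without replacement would suppress the statistics, assuming the SAP 7.3 minimum applies. Concentration listings, summaries and plots are not affected, so the parameter table can be rerun. The correction should be made before database closure, because it fixes the denominator of a primary table.

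**What to change.** In SAP 8.2.1, replace the single citation with two:

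- Section 5.1.3 for the plasma PK parameters (Tables 1 and 3).
- Section 5.1.2 for the 14C recovery measures (Section 6.3.1 and the two urine 14C parameters in Table 2).

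In SAP 5.1.3, define the set by treatment only and drop the reference to randomization. Its mention of three matrices can stay: a participant who qualifies only through urine or feces has plasma parameters coded as not calculated, and SAP 7.3 sets these to missing.

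The cost is one citation sentence and one wording change in the SAP. No data collection or protocol change is needed.
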